TABLE 2

	A. Placebo Group			B. Gabapentin Group		
	AM	Noon	PM	AM	Noon	PM
Day 1	PLC	PLC	PLC/PLC	PLC	PLC	PLC/GBP
Day 2	PLC	PLC	PLC/ PLC	GBP	PLC	PLC/GBP
Day 3	PLC	PLC	PLC/ PLC	GBP	GBP	PLC/GBP
Day 4	PLC	PLC	PLC/ PLC	GBP	GBP	PLC/GBP
Day 5 - 112	PLC	PLC	PLC/PLC	GBP	GBP	GBP/GBP
PLC =Placebo GBP =Gabapentin 300 mg						

Compliance with gabapentin and placebo will be monitored by the addition of 25 mg of riboflavin to each of the four daily study medication capsules. Subjects will be informed not to take any vitamins other than those that do not contain riboflavin. Baseline urine will be collected on each subject at two times to establish a reference

point for each subject. Urine riboflavin measurements will be obtained at each research assessment time, as stated above, for a total of 11 samples per subject to provide an overall assessment of study medication compliance and to examine for differential effects between treatment groups. Although not as reliable, pill counts of remaining medication at each treatment visit will be done as an ancillary measure of subject compliance and analyzed separately. All medications will be placed in blister cards with days of the week printed to assist in subject compliance. The MM provider will review these blister packs with each subject at study visits to monitor and enhance compliance.

Proton Magnetic Resonance Spectroscopy (¹H-MRS) for Glutamate and GABA: This will occur prior to randomization (see above) and again at week 3 (window between days 17-24) of study medication between 2-4 hours after the last gabapentin/placebo dose to standardize acute dosing effects. Subjects will be breathalyzed prior to the scan and need to be zero (or will be rescheduled ASAP), and, if smokers, the time of last cigarette will be recorded. In an ongoing trial we have found no problems with imaging (fMRI) clinical trial participants twice (baseline/week 3) – very few have to be rescheduled due to drinking and some subjects find it intriguing. Each scan takes about 60 minutes and uses the following protocol: A structural scan will be taken for ¹H-MRS voxel placement and tissue segmentation (256 sagittal slices; 1mm thick/50% gap). The ACC voxel for ¹H-MRS will be placed on midsagittal T1-weighted images, anterior to the genu of the corpus callosum, with the ventral edge of the voxel aligned with the dorsal edge of the genu and a voxel size of 3 x 2.5 x 2.5 cm³ will be selected (consistent with Umhau, 2010 and Mon, 2012). Following auto-shimming, single-voxel water-suppressed ¹H-MRS spectra will be acquired using a Point Resolved Spectroscopy (PRESS) sequence: Repetition Time (TR) = 2000ms; Echo Time (TE) = 40ms; number of averages = 256); an unsuppressed water spectrum will be co-acquired (TE = 40ms, number of averages = 16), scaled for partial volume effects and relaxation, and used as a concentration reference. This sequence has been shown to

perform superiorly to other PRESS sequences (TE = 30ms, 80ms; TE-averaged; (Mullins, 2008)) for imaging glutamate. Analysis of PRESS data will be conducted using LC Model 6.3 (Provencher, 1993), an operator-independent curve-fitting software package that uses least-squares estimation for quantifying metabolite concentrations; the basis set for TE = 40ms is provided by the vendor and includes myo-inositol, gamma-aminobutyric acid (GABA), lactate, taurine and aspartate, creatine, glutamine, glutamate, N-acetylaspartate (NAA), N-acetylaspartate-glutamate (NAAG), and phosphocholine (Cho). Although glutamate resonances are historically challenging to isolate, simulation research has demonstrated that glutamate can be measured with a similar level of reliability as NAA using the proposed acquisition parameters (PRESS with TE = 40ms, VOI = ACC, field strength = 3T) (Mullins, 2008). Although a TE = 40 PRESS acquisition sequence is ideal for imaging glutamate, it is not suitable for imaging GABA because, using standard acquisition protocols, GABA MRS peaks are greatly overshadowed by nearby creatine and choline MRS peaks. As a result, we will acquire a separate GABA MRS scan using the state-of-the-art MEGA-PRESS j-editing technique for isolation of GABA (Mescher, 1998). This sequence (TR = 1500ms; TE = 68ms; number of averages = 256) alternately applies a frequency-selective editing pulse at 1.9 ppm and 7.5 ppm, in an interleaved fashion; subtracting these spectral pairs produces a spectrum with a GABA peak that is clearly separated from the larger surrounding creatine and choline signals. *Analysis of MEGA-PRESS data will also be conducted using LC Model; the latest version of the software (i.e., 6.3) provides a simulated basis set and specialized routines for quantifying GABA metabolite concentrations.*

Only metabolites with fitting uncertainties (Cramer-Rao Lower Bound values) < 20% of SD in the LC Model output will be retained for analysis. LC Model includes standardized zero filling, Fourier transformation, and automated phase, baseline, and eddy current correction. To address variability in within-voxel tissue composition we will: 1) co-register T₁-weighted images to their scout images and correct for b₁ field bias, 2) extract and segment T₁-weighted images into partial volume maps of gray matter (GM), white matter (WM), and CSF using FMRIB Software Library (FSL) tools, 3) match the coordinates and size of the ¹H-MRS voxel with the segmented images and extract the tissue fractions within the voxel using FSL tools, 4) correct the raw values obtained from the LC model (scaled to water) for CSF and coil loading (Michaelis, 1993), and 5) calculate each participant's GM to brain matter (BM) ratio (i.e., GM:BM = GM/[GM+WM]) for use as a covariate in statistical analyses. This calculation will be made separately for each metabolite of interest because the spatial region that each metabolite is localized to is not the same due to the chemical shift artifact. The particular displacement of a given metabolite's localization region is determined by the metabolite's chemical shift divided by the product of the strength of the gradient used to localize the voxel and the gyromagnetic ratio for protons. For each metabolite, in each participant, we will match the coordinates and size of the voxel (accounting for chemical shift displacement) with the segmented images and extract the tissue fractions using FSL tools. Metabolite concentration estimates will be corrected for T₁ and T₂ relaxation effects using established literature values (Mlynarik, 2001; Wansapura, 1999) and scaled to water. Following this procedure we have produced the following example spectra:

FIGURE 3. LC Model Spectra for Glutamate

[figure not shown]
[figure not shown]

FIGURE 4. LC Model Spectra for GABA

We have run 6 healthy controls *through the PRESS MRS sequence* and found a mean (SD) glutamate, as a ratio to water, of 7.66 (1.24) or as a ratio to creatine, 1.38 (0.15). *We have run an additional 7 healthy controls through the MEGA-PRESS MRS sequence and found a mean (SD) GABA, as a ratio to water, of 1.75 (0.19). These values are consistent with published levels (where there is a range of values based on quantification method and reference analyte).*

Lab and Genetic Assays: The CNL lab directed by [name] has 20 years of experience in measuring carbohydrate deficient transferrin (CDT) and currently runs a state-of-the-art HPLC based assay that is recognized by the IFCC as a candidate reference method (Helander, 2010). The analyte of interest is disialo-CDT as a percentage of total transferrin (%dCDT). Extensive quality control and proficiency testing is routinely performed. His lab also assays urinary Ethylglucuronide (EtG), a sensitive measure of any/low alcohol consumption using a Microgenics immunoassay which correlates highly with LC-MS. Qiagen DNA extraction kits are used to extract DNA from whole blood by a dedicated genetic technician in his lab, tested for DNA purity, and used in Taqman PCR analysis with specific probes and primers purchased from Life Science Technologies using a Step One analyzer (Applied Biosystems). His K05 funding allowed him to become proficient in this type of analysis (Anton, 2012) and he has genotyped hundreds of samples with various SNP's and VNTR's including the glutamate and GABA genes of interest (see background section).

Outcome Variables and Power Analyses: The primary drinking outcome variable will be the percent of subjects with no heavy drinking days (PSNHDD) as defined by Falk (2010), chosen because it is currently accepted by the FDA in its guidance for clinical trials and also is consistent with our prior work with gabapentin. However, other secondary drinking variables such as percent days abstinent, % heavy drinking days, and drinks per day, as well as craving (OCDS) and biomarkers (%dCDT and GGT) will be calculated and reported for completeness sake. Urinary riboflavin and pill counts will be used as measures of compliance and compared between groups while potentially serving to define compliers for independent analysis. PSQ, POMS, and MES will evaluate sleep quality, mood state, and medication effect differences between medication groups. Pre-randomization and week-3 brain glutamate and GABA levels will be calculated for each subject and their change will be the unit of measurement for the treatment effect mediator analysis (see below).

A statistical power calculation was conducted using data from our past two studies (background section) using the treatment effect in subjects with a DSM-IV history of AW on the PSNHDD outcome variable. With 45 subjects per medication group (total N=90) the power to detect the gabapentin treatment effect on PSHDD is between .83 (study 1 calculation) and .98 (study 2 calculation). While significant covariate effects in our earlier studies have not been observed with this outcome variable, additional power analysis using Monte Carlo simulation (n=500) in the presence of covariates modeled, (e.g. pretrial drinking, OCDS, ADS, etc.) on our previous studies was conducted. Power values comparable to those in the simpler analysis were found in all cases ranging from .81 to .87 (study 1) to .95 to .99 (study 2).

The statistical power calculation for gabapentin's effect on brain glutamate change from baseline to week-3 is based on the work of Umhau (2010), the study design closest to our own, where an acamprosate-induced change in brain glutamate levels (vs. placebo) was detected with an effect size of .95. *The power to detect a similar gabapentin vs. placebo difference in the current proposal with an n=45/group is in excess of .99 with the ability to detect an effect size as low as $d = .6$ with power of .8. Since the reported effect of gabapentin on GABA is quite large (Cai, 2012; Kuzniecky, 2002; Petroff, 1996; Petroff, 2000) the power to detect a gabapentin vs. placebo difference with an n=45/group is in excess of .9. Given this large statistical power, an expected maximal 10% attrition due to inadequate scans should not materially affect our ability to detect a medication effect on glutamate or GABA. Additionally, there is likely to be sufficient variation in both medication response and brain glutamate/GABA level change to allow acceptable use of a mediation analysis to examine the effect of this glutamate/GABA change on treatment response.*

Power has not been calculated for the exploratory genetic analyses. The genetic SNP's we have chosen to explore are not only indicated by the literature but also, importantly, have a reasonable genotypic distribution. Given our past work and HapMap data (see Preliminary Data section) we expect the distribution of both the *GABRA2* and *GM8* allele frequencies to be about 60:40 with not much difference between Euro-Caucasians and African Americans. This should provide a good balance between treatment groups. Modifier effects are likely to be observable if the effect size is moderate to large. In any case, this data will allow more appropriate power calculations for subsequent studies. Effects of genetic variation on brain glutamate/GABA are unknown and completely novel but as a main effect with 90 subjects (even accounting for drop-outs or unusable scans) the power to detect a gene by analyte effect should be sufficient if clinically meaningful.

Data Analysis Plan: *The PSNHDD (with baseline percent heavy drinking days as a covariate) will be analyzed with a multiple logistic regression with indicator coding medication group as the primary independent variable. All hypotheses (primary, secondary) will be assessed with likelihood ratios. Other possible pre-randomization variables, e.g. sex, smoking status, ADS score, pre-randomization CIWA-Ar score, etc. will be evaluated as possible covariates in the final analysis. Missing data (assuming monotonicity) will be imputed as heavy drinking days. In addition, the relapse time-course will be analyzed by GEE techniques for the full treatment X time factorial design. Secondary outcome variables, e.g. other drinking variables, OCDS, POMS, PSQ index, MES and biomarkers (%dCDT and GGT), will be analyzed as either mixed models (SAS PROC MIXED) or in GEE analyses (SAS GENMOD) depending upon the nature of the variable (parametric or categorical).*

Change in glutamate and GABA levels will be analyzed as a mixed model (SAS PROC MIXED) with time as a within subject variable and medication group as between subject variables. Significant interactions will be interpreted with simple effects and main effects will be assessed in the absence of the interaction. If sex and smoking status (reported by some to effect brain GABA levels), or pre-randomization CIWA-Ar score are found to significantly influence glutamate or GABA levels, or if their inclusion reduces residual variance, they will be included in the model as covariates.

In order to assess the degree to which changes in brain GABA and glutamate account for drinking outcomes, neurochemical variables (as difference scores) will be entered into the main logistic regression model. A reduction in the significance of the main treatment effect or the treatment by time interaction will be suggestive of a mediation effect. Path analysis will be used to test the significance of the indirect path from treatment to GABA/glutamate levels to relapse status and/or other drinking measures.

Timeline: Since our staff is trained in all procedures and scales are digitalized, the first 3-4 months will be used for medication production, database building, and data collection computer tablet study specific program production. In the first year we will screen/randomize 38/18 subjects and then 57/27 subjects in year 2-3 and 38/18 subjects in year 4. The last five months will be used for data analysis and publication production.

Interpretations and Future Directions: While this study will focus on gabapentin efficacy in those with a history of AWS, it is possible that it might have anti-craving and reinforcement effects *independent of effects based on AWS history*. Since this proposal will not include those without a history of AWS we will not be able to address the issue of broader efficacy directly. However, using exploratory analysis on craving effects, reasons for drinking and medication effects scales, as well as sleep, we might discover mediators of treatment efficacy that could be studied in expanded populations in the future. Also, baseline levels of brain glutamate/GABA cannot be compared with levels in alcohol dependent individuals without a history of AW. Nevertheless, the ability to relate drinking outcome to changes in these levels and ability to relate the efficacy of gabapentin to glutamate/GABA brain changes would still be salient and important, as would the pharmacogenetic exploration. Since the complete understanding of brain glutamate/GABA levels as measured by ¹H-MRS is evolving, it is possible that those with AW might have less glutamate and more GABA prior to randomization since the pools measured might exist mostly in the intra-cellular space due to auto-regulatory mechanisms and/or sequestration, but still might change during treatment. The directionality of the effect will not negate the potential to observe changes based on gabapentin treatment and the relationship of those changes to efficacy. It will add data to the growing literature that could, in fact, assist in correct interpretation of the localization of these brain neurotransmitters. Furthermore, even if gabapentin is not found efficacious, the difference in brain glutamate and GABA levels change over time, especially in relationship to relapse status, would still add new information about AW biology and prognosis *that could be useful for future drug development*. The collection of DNA on all subjects will allow future explorations including deeper sequencing and epigenetic/regulatory changes of the candidate genes proposed, as well as exploration of other genetic variation that might emerge in relationship to relapse and medication response. *If these results are positive, future studies might investigate more specific pharmacological treatment matching between those with and without a history of alcohol withdrawal symptoms.*

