In an exploratory study (study 1) our group evaluated a commercial procedure (the combined use of acute flumazenil and six weeks of gabapentin) being marketed for alcohol dependence (Anton, 2009). While initially agnostic about the utility of this approach, it provided the opportunity to explore the use of gabapentin in a structured fashion with the a priori hypothesis that this treatment would work, if at all, only in those with pre-treatment alcohol withdrawal symptoms. The theory underlying the use of IV flumazenil was that 1) it has been shown in a few, but not all, studies to ameliorate AW symptoms and 2) that it reversed the chronic effect of alcohol on GABA-A receptors (Biggio, 2007; Sanna, 2003) allowing them to be more responsive to GABA signaling. Since gabapentin had been shown previously to be useful for the treatment of AW (Myrick, 2009), and as it purportedly normalizes GABA/glutamate balance/tone in the brain, it was hypothesized to work in conjunction with flumazenil to "reset" and "maintain" normal GABA and glutamate tone resulting in less craving and relapse. Armed with this information, we randomized 60 alcohol dependent individuals in a double blind fashion to receive either active flumazenil infusions (2 consecutive days) and gabapentin up to 1200 mg/day or their matching placebos for approximately six weeks. Individuals who drank up to 72 hours prior to randomization were evaluated for alcohol withdrawal using the Clinical Institute Withdrawal Assessment – Revised (CIWA-Ar) (Sullivan, 1989) and urn randomized to the medication groups based on a CIWA-Ar score (below or ≥ 7), *with only 3 people having scores of 10 or more*. Participants were assessed for alcohol withdrawal on the first two days of treatment and drinking was assessed weekly by the timeline follow-back calendar method, with %CDT (a marker of relapse drinking) measured at baseline, week-3, and end of study. We found a significant ($p= 0.021$) effect favoring active treatment in reducing CIWA-Ar scores in the first two days of treatment. Importantly, we found no main effects of medication treatment on any drinking measure but a significant interaction of medication group by pre-randomization AW score, such that percent days abstinent ($p= 0.0006$), percent of individuals completely abstinent ($p=0.002$), time to first heavy drinking day ($p= 0.06$) and %CDT ($p=0.001$) all favored the active medication group in those with high pre-randomization CIWA-Ar scores (about 20% of subjects). Findings were similar when expanding and comparing those with and without a positive DSM-IV AW item (43% of subjects) (see Figure 1). The odds ratio for DSM-IV AW positive individuals not relapsing when treated with active medication vs. placebo was 3.2 (95% CI 1.4 - 7.4). Also, while there was more baseline drinking in those who were DSM-IV AW positive, co-varying various baseline drinking and severity (ADS, OCDS) measures did not impact the significance of the active medication vs.

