
placebo effect, suggesting it was the AWS history itself that was important in predicting outcome and not recent drinking levels or alcohol severity. This novel finding of DSM-IV positive AW subjects possibly responding to gabapentin alone opens a treatment option for more individuals and is the basis of this proposal.

[figure not shown]
FIGURE 1. Proportion non-relapsed based on pre-randomization DSM IV history of AWS (negative or positive) treated with Placebo or a combination of IV Flumzenil (FMZ) plus oral Gabapentin (GBP)

The Interaction between AW status and medication group ($X^2(1) = 7.61, p = .006$)

In another study (study 2) funded by NIAAA, we evaluated the effect of adding gabapentin to naltrexone, compared to naltrexone alone or placebo with the hypothesis that gabapentin given during the first 6 weeks of a 16-week naltrexone trial would improve drinking outcomes based on reduction of early abstinence effects (sleep problems, irritability, etc.). In this study (Anton, 2011), 150 alcohol dependent individuals were randomized to naltrexone (50 mg/day) and gabapentin (1200 mg/day), naltrexone alone plus placebo, or double placebo. Gabapentin/placebo was given for 6 weeks and naltrexone/placebo was given for 16 weeks. Individuals received Combined Behavioral Intervention (CBI), Medical Management (MM), and assessments as described in the COMBINE Study (Anton, 2006). *The initial results favored the naltrexone-gabapentin group over the other two groups (p values 0.001 to 0.04 for different drinking outcomes), especially during the gabapentin phase (first 6 weeks) of the study.*

FIGURE 2. Proportion non-relapsed with a pre-randomization DSM-IV history of AW treated with placebo or naltrexone plus gabapentin.

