However, effects faded over time once gabapentin was stopped. Further exploratory analysis of the data suggested that gabapentin had the greatest efficacy in those with a history of AWS (see Anton, 2011). Based on study 1 results, and to obtain further preliminary data for this proposal, we recently reanalyzed the data based on meeting DSM-IV AW criteria (SCID AW Item, current and historical). Within the group who were positive for a history of AW (56% of subjects), the effect of gabapentin over placebo on the percent subjects with no heavy drinking day was $p = 0.017$ with an OR of 4.4 (95% CI 2.4 – 7.9). For illustration, time to relapse to a heavy drinking day is depicted in **figure 2**. There was no significant effect of ntx/gbp in those without an AW history and/or those with an AW history treated with naltrexone alone ($p > 0.05$, data not shown). Also, although DSM-IV AW positive individuals had higher baseline drinking and severity, co-varying these variables did not significantly alter medication efficacy, findings consistent with study 1.

Also, using a “Reasons for Drinking Scale” that we devised to evaluate why people drink: items dealing with pleasure, liking high, stress, feeling normal, habit, and relief (avoiding feeling bad, nervous, irritable, and insomnia), those scoring higher on “relief drinking” responded better to naltrexone/gabapentin than placebo or naltrexone alone ($p=0.001$). This also supports the idea that gabapentin works in those with a history of AW symptoms compared to those without.

While these studies suggest that gabapentin is likely to be efficacious in relapse prevention and drinking-reduction in those with a history of AW symptoms, they are limited in several important ways: **1) gabapentin was not given by itself, 2) it was given for only 6 weeks in study 2 and relapse occurred after it was stopped, 3) in study 2, individuals were not randomized based on AW history and the analysis was post-hoc.** Therefore, it is important to do a proper 16-week prospective placebo-controlled trial of gabapentin alone in those with a history of AW in order to confirm its efficacy in this important subgroup of alcohol dependent individuals. This is the primary objective of this proposal.

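### Study 2's p-value and 95% confidence interval for the odds ratio of 4.4 disagree as labelled, and the power attributed to studies 1 and 2 is not reproduced at their printed odds ratios under two-sided .05

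*Combined protocol and SAP*

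**What the plan says.** All places are in the combined protocol and SAP.

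- **Preliminary Data Supporting Significance, study 2, design:** "150 alcohol dependent individuals were randomized to naltrexone (50 mg/day) and gabapentin (1200 mg/day), naltrexone alone plus placebo, or double placebo".
- **Same section, reanalysis by AW history:** the contrast is introduced as "Within the group who were positive for a history of AW (56% of subjects), the effect of gabapentin over placebo", and its result is given as "no heavy drinking day was $p = 0.017$ with an OR of 4.4 (95% CI 2.4 – 7.9". No model is named and no counts are given.
- **Same section, study 1:** the odds ratio for not relapsing, "active medication vs. placebo was 3.2 (95% CI 1.4 - 7.4".
- **Outcome Variables and Power Analyses:** the calculation used data from these two studies, "using the treatment effect in subjects with a DSM-IV history of AW on the PSNHDD outcome variable". With 45 per group, "the power to detect the gabapentin treatment effect on PSHDD is between .83 (study 1 calculation) and .98 (study 2 calculation". A simulation with covariates gave .81 to .87 (study 1) and .95 to .99 (study 2). The section states no odds ratio, placebo rate, alpha, sidedness or test.
- **Data Analysis Plan:** "All hypotheses (primary, secondary) will be assessed with likelihood ratios".

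**The concern.** An odds ratio, its 95% interval and its p-value from one analysis are tied together by a single standard error. Here the interval and the p-value imply standard errors that differ by a factor of two, and no other part of the document explains the difference. Read at face value, the interval puts the lower limit for the study 2 effect at 2.4. The p-value puts it near 1.3. The pilot evidence therefore looks more certain than its own p-value allows.

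This is more than a slip in background text because study 2 is a named source of the effect behind the stated power. That invites a second, separate check: do the printed odds ratios give the stated power? The text leaves out the inputs needed to tell.

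**Working it through.** **1. Study 2: interval against p-value**

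Inputs: OR 4.4, limits 2.4 and 7.9, p = 0.017 (Preliminary Data, study 2). The geometric midpoint of the limits is √(2.4 × 7.9) = 4.35, so the estimate and limits fit each other. The conflict is with p.

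- *From the interval:* SE = ln(7.9/2.4)/(2 × 1.96) = .304; z = ln(4.4)/.304 = 4.87; two-sided p = 1.1e-6. Rounding of the three printed figures moves p only between 5.0e-7 and 2.3e-6.
- *From the p-value, two-sided:* z = 2.387; SE = ln(4.4)/2.387 = .621; 95% interval = exp(ln 4.4 ± 1.96 × .621) = 1.30 to 14.9. Rounding leaves the lower limit at 1.3 and moves the upper limit between about 14.5 and 15.2.
- *Ratio of standard errors:* .621/.304 = 2.0.

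Other readings do not close the gap. A one-sided p of 0.017 gives 1.1 to 17.3, which is wider still. Treating 2.4 to 7.9 as a 90% interval gives p of about 4e-5. An interval of ±1 SE at p = 0.017 runs from 2.37 to 8.19, close to the printed limits but not an exact match. Read the other way, 2.4 to 7.9 as ±1 SE gives SE .596 and p = .013.

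**2. Which figure is more likely wrong**

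Assumption: one yes/no per subject, as the description of the outcome reads. The smallest possible SE of a log odds ratio, over all event rates and splits of N subjects, satisfies SE² = 4/(N·q(1−q)), with q = 1/(1+√OR). At OR 4.4, q = .323 and q(1−q) = .2186.

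| N | Basis | Smallest SE | Narrowest 95% interval |
|---|---|---|---|
| 84 | 56% of 150, all three arms | .467 | 1.8 to 11.0 |
| 150 | every subject in study 2 | .349 | 2.2 to 8.7 |

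An SE of .304 needs N = 4/(.2186 × .304²), about 198 subjects (189 after allowing for rounding). On this reading the printed interval is tighter than the whole of study 2 could support.

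**3. Stated power against the printed odds ratios**

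Inputs: 45 per group; ORs 4.4 and 3.2; the likelihood-ratio test named in the Data Analysis Plan. Assumed: alpha .05, two-sided, with one-sided shown as well. For each placebo rate p0 from .02 to .90, the gabapentin rate is OR·p0/(1 − p0 + OR·p0). Power is the exact sum of binomial probabilities over all tables in which the test rejects in favour of gabapentin.

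| OR | Stated power | Maximum, two-sided | Maximum, one-sided |
|---|---|---|---|
| 4.4 (study 2) | .98 | .926 (p0 = .325) | .970 |
| 3.2 (study 1) | .83 | .764 (p0 = .36) | .874 |

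Two-sided power at placebo rates .10, .20, .30 and .40 is about .79, .91, .93 and .92 at OR 4.4, and .54, .72, .76 and .76 at OR 3.2.

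Normal approximations give two-sided maxima of .933 (pooled) to .949 (unpooled) at OR 4.4, and .775 to .799 at OR 3.2. One-sided at OR 4.4 they give .967 to .974. With the OR at the top of its rounding range (4.449), the unpooled one-sided figure is .976, which rounds to .98.

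The smallest OR that reaches .98 is about 5.8 two-sided or 4.8 one-sided. For .83 it is about 3.5 two-sided or 2.9 one-sided.

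**The case against.** **One analysis with a wrong label could nearly explain the figures.** A reader might infer that the p-value and interval must come from two different analyses. The document does not support that: a single analysis whose limits are about ±1 SE comes close to both. What is shown is a conflict as labelled, and the cause is unknown. If that explanation is right, the 95% label is still wrong.

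**The width of a pilot interval does not enter a power calculation.** This stands. Power depends on the assumed effect, and the power section cites neither the interval nor the p-value. The conflict does not move OR 4.4 or N = 90. The text also describes the study 2 analysis as exploratory and post hoc.

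**The power inputs may not have been the printed odds ratios.** This also stands. The section says only that data from the two studies were used. Figures 1 and 2 plot proportions not relapsed by arm and are missing from the text available here, so placebo rates may be shown there.

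**Under a one-sided test the shortfall almost disappears.** Largely true: .83 is then reachable, and .98 is missed by about a point or met by rounding under an unpooled approximation. A reader might infer from the two-sided maxima that the stated power is wrong or the trial too small. The document does not establish either, because it gives no alpha, sidedness or rates.

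**The estimate may not be a crude odds ratio.** No model is named, and the text mentions analyses with covariates. That limits step 2 of the working, which needs the yes/no reading. It does not touch step 1. In study 1, 43% of 60 is about 26 subjects; the smallest SE for a crude OR of 3.2 is then .818, against .425 implied by the printed interval. This remains a query about the type of estimate, since the document cannot settle it.

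**Conclusion.** The study 2 p-value and interval are inconsistent as labelled, by a factor of 2.0 in the standard error. This needs no assumption about counts, arms or event rates beyond the usual normal approximation on the log-odds scale. That the interval is the likelier error is conditional on one yes/no per subject; a ±1 SE range is a possible but unproven cause.

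The power point is separate and conditional. If the printed odds ratios were the inputs and the test is two-sided at .05, the stated .98 and .83 should read at most about .93 and .76. Under one-sided .05 the ceilings are about .97 and .87. As written, a reader cannot tell which effect, rate or test produced the stated values. The correction is worth making because the trial relies on these power figures, but nothing here calls for a change to the sample size.

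**What to change.** 1. **Preliminary Data, study 2.** Recheck the estimate in AW-positive subjects from the data in hand, name the model, give the counts by arm, and print a p-value and 95% interval that agree. If OR 4.4 and a two-sided p of 0.017 are confirmed, the interval is about 1.3 to 15.
2. **Outcome Variables and Power Analyses.** Recompute the power from the reconciled effects and restate it. Give the effect used (odds ratio or proportions), the placebo rate, alpha, sidedness and test.
3. **Preliminary Data, study 1 (query only).** State what type of estimate 3.2 (1.4 to 7.4) is.

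The cost is one recomputation from existing data, one corrected line in the background and one or two sentences in the power section. N = 90, the endpoint and the planned analysis do not change.
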